Principal Investigator: [name].

Co-Investigators: (including VA and WOC staff): While all research staff are trained to obtain informed consent, those identified with an asterisk (*) will obtain informed consent for this study. The PI and the listed research team will have access to PHI.

Co-Investigators: [name]., Ph.D., [name]., [name]., [name]. [name], [name], [name] [name]

Authorized Prescribers: [name]., [name]., Ph.D., [name]., [name] [name]

Nursing Staff: [name], R.N.,

Psychologists: J. [name].

Research Staff: [name], [name], [name], [name], [name]

Title of Project: Buprenorphine/Naloxone Treatment for Prescription Opioid Dependence

Purpose: Although buprenorphine/naloxone (BUP/NLX) treatment is effective for the treatment of prescription opioid dependence, previous studies have not determined the optimum dose of BUP/NLX for this patient population. The goal of this study is to determine if there are differences in clinical efficacy of BUP/NLX tablet in low dose range (less than or equal to 8/2mg) vs. high dose range (greater than or equal to 16, range 16-24mg). The main outcomes of interest will be treatment retention, use of opioids, and the use of other drugs of abuse.

Introduction:

Prescription opioid abuse, including oxycodone, hydrocodone, hydromorphone, morphine, codeine, propoxyphene, and methadone, has emerged as a major public health problem particularly in the United States, which represents about 5 percent of the world's population but consumes 80 percent of the global opioid supply and 99 percent of the global hydrocodone supply (Sehgal et al., 2012). Prescriptions for opioid medications have increased dramatically with 174 million prescriptions dispensed from retail pharmacies nationally in 2000, increasing to 257 million prescriptions by 2009 (Food and Drug Administration (FDA), 2010). According to data from the Centers for Disease Control and Prevention ((CDC), deaths due to prescription opioids went from 1.3 per 100,000 in 1999 to 5.0 per 100,000 in 2008, resulting in 14,800 prescription painkiller deaths in 2008 (Centers for Disease Control and Prevention, 2012).

Furthermore, deaths from prescription opioids have dramatically increased over the past 10 years and are now the second leading cause of accidental death in the US (Okie, 2010).

Unlike other drugs of abuse, prescription opioid medications are primarily obtained from physicians, friends or family members and/or the Internet, rather than through drug dealers.

Recently, there has been an increase in non-medical abuse of prescription opioids, defined as use without a prescription and/or in a manner other than intended or prescribed, with more than 12 million people reporting using prescription opioids non-medically in 2010 (SAMHSA, 2012).

The use of opioid prescription drug use has also recently been shown to be a "gateway" to use of heroin (Jones, 2013). These figures underscore the importance of development of treatments for prescription opioid dependence.

Buprenorphine as a treatment for opioid dependence

Buprenorphine, a derivative of the opiate alkaloid thebaine, is a partial μ -opioid agonist and a weak κ -opioid antagonist (Walsh and Eissenberg, 2003). In clinically used doses, buprenorphine effects are similar to the full μ -opioid agonist like morphine or methadone. At higher doses, however, the effects of buprenorphine plateau, and it acts like an opioid antagonist. This “ceiling” effect of buprenorphine decreases the risk of overdose even at high intravenous doses and limits its abuse liability (Walsh and Eissenberg, 2003). In addition, its slow dissociation from the opioid receptors allows flexible dosing ranging from several times a day to three times per week. Buprenorphine, formulated as a sublingual tablet or film, is available alone or in a combination tablet containing Buprenorphine and Naloxone in a ratio of 4:1 (Johnson et al., 2003). Since naloxone is poorly absorbed when taken orally or sublingually, naloxone effects are negligible when the medication is taken as directed. However, injection of this combination in dependent individuals would precipitate opioid withdrawal symptoms due to naloxone effects, and deter diversion of this product to injection drug use. A large number of studies have demonstrated the efficacy of buprenorphine as an agonist treatment in opioid dependent individuals. However, it is important to note that the majority of studies supporting the efficacy of BUP/NLX for opioid dependence were conducted in heroin-addicted patients.

Buprenorphine as a treatment for prescription-opioid dependence

Only a few studies systematically examined the characteristics of prescription-opioid dependent individuals as compared to those who are heroin dependent. Prescription-opioid dependent patients, compared to those who are dependent on heroin, are younger, have fewer years of opioid use, and are less likely to have a drug treatment history (Moore et al., 2007). Further, prescription opioid dependent patients, compared to heroin only, or heroin and prescription opioid users, are more likely to stay in buprenorphine treatment and have better treatment outcomes (Moore et al., 2007).

A recent study by Weiss et al. assessed the efficacy of a combination of the opioid substitute buprenorphine/naloxone (BUP/NLX) in 653 prescription opioid dependent patients (Weiss et al., 2011). In that study, subjects received standard weekly medical management with or without intensive opioid dependence counseling. The study had two phases: Phase 1: 2-week stabilization, 2-week taper, and 8 week post-medication follow-up. The main finding of the study was, out of 653 patients, 43 (6.6%) had a successful urine-test-confirmed outcome of no opioid use after phase 1 of treatment. Further, of the 360 patients who underwent phase 2, 177 (49.2%) had a successful outcome at week 12 of treatment, but this fell to just 31 (8.6%) at the 8-week follow-up visit. There was no difference observed between those who received adjunct counseling and those who did not. These findings are promising for the utility of BUP/NLX for prescription opioid dependence, but they also suggest that more effective treatment approaches are needed.

It should be noted that despite the prevalence of opioid dependence among military personnel and Veterans, there are no studies evaluating buprenorphine for opioid dependence in the Veteran population. Further, assessment of psychiatric symptoms among those with commonly occurring disorders, such as depression and post traumatic stress disorder (PTSD) have also not been systematically evaluated.

Proposed study: As summarized above, BUP/NLX treatment seems to be moderately effective for the treatment of prescription opioid dependent patients. The Weiss et al. study did not address if BUP/NLX is more effective in a lower or higher dose range (Weiss et al., 2011). The 16/4 mg of BUP/NLX was the most commonly prescribed dose. In a recent meta-analysis of BUP/NLX studies for opioid dependence (Fareed et al., 2012), higher doses of BUP (16mg or higher/day) were associated with better treatment retention and reduced opioid use than the lower dose range (less than 16mg/day). However, to our knowledge, no previous study has examined the optimum dose of BUP/NLX in prescription-opioid dependent patients.

Subjects: We plan to enroll approximately 200 participants. Veterans who meet the following criteria will be eligible for participation: 1) Males and females between the ages of 18 to 65, current dependence on prescription opioids as evidenced by fulfilling DSM-V criteria for Opioid Use Disorder, signs of opiate withdrawal as evidenced by a COWS score of 7 or greater, self-reported history of opioid dependence, and a positive urine toxicology for opiates; 2) willingness to be detoxified from opioids for buprenorphine maintenance ; 3) for women of childbearing age, a negative pregnancy test at screening with agreement to use adequate contraception to prevent pregnancy, with monthly pregnancy tests obtained during study participation. Exclusion criteria: 1) use of heroin for more than 4 days in the past month; 2) lifetime history of opioid dependence due to heroin alone; 3) ever used heroin intravenously; 4) requirement for current ongoing opioid treatment for adequate pain management; 5) current alcohol, benzodiazepine, barbiturate use with physiologic dependence as determined during screening history and physical, 6) serious unstable medical illness including bradycardia or other arrhythmias, major cardiovascular, renal, endocrine, or hepatic disorders for which buprenorphine treatment is contraindicated or which at the determination of the MD is medically dangerous; 8) serious psychiatric illness including psychosis, bipolar disorder with psychosis; 9) significant current suicidal or homicidal thoughts necessitating a higher level of care; 10) known allergy or intolerance to buprenorphine. Please note that individuals with commonly occurring psychiatric disorders, such as depressive disorders and post traumatic stress disorder, will be included in this “real world” study.

Privacy: All information that is obtained from subjects will be used for the specifically stated purposes that are described in this Project Description and have been approved by the HSS. The personal identifiers that are necessary for this research and that will be obtained are the following: Name, Medical Record Number, Social Security Number, Age, Gender, Medical and Psychiatric History, and Laboratory Examination. The procedures for data collection and recruitment of subjects, described elsewhere in the Project Description, are the least intrusive consistent with obtaining the information necessary to complete this project. All members of the research team will review, use, and record the minimum amount of information necessary to accomplish the goals outlined in the protocol. All members of the research team have been trained on VHA privacy regulations and policies and training are current. The settings in which informed consent discussions, other subject interviews or research procedures occur will provide the same privacy protections that would exist if these discussions, interviews, or procedures were carried out for required clinical care (private rooms, drawn curtains, etc.). The information will be used for this project, or disclosed to others, only as permitted by the Privacy Act, the HIPAA Privacy Rule, and VA policy.

Selection: Veterans will be recruited through VA clinics and from the New Haven area by newspaper advertisements and flyers. After the initial phone screening, potential subjects will undergo a comprehensive evaluation that will include medical, psychiatric, and drug use histories as well as physical, psychiatric, and laboratory examinations. Laboratory examination will include CBC, liver and thyroid function tests, serum electrolytes, BUN, creatinine, PT, PTT, RPR, random glucose, urine analysis (including urine pregnancy for women), and urine toxicology screening.

Research Plan:

This will be a randomized, open-label clinical trial. Veteran opioid dependent men and women will be randomized to one of two treatment groups: low dose range of BUP/NLX (Less than or equal to 8mg) vs. high dose range of BUP/NLX (Greater than or equal to 16mg). During induction into buprenorphine, all participants will be started at a dose of 2mg, and this dose will be increased as needed for stabilization of opioid withdrawal symptoms, up to 8mg for the low dose group, and up to at least 16mg for the high dose group, within about 7 day period. If a participant is randomized to the low dose group but is experiencing withdrawal symptoms that cannot be stabilized the participant will be discharged from the study. Participants will be clinically managed and will get monthly assessments. Participants will be seen on a daily basis (excluding weekends) for the initial 7 day induction. Once subjects are on maintenance dose of BUP/NLX (goal is within 5 days), they will be seen weekly by study RN for medical management, symptom evaluation, and medication refill. Participants will also complete study questionnaires at this time. At the end of the 12-week study, participants will either be referred to a buprenorphine clinic if they wish to continue this medication, or if they wish to be drug free, will undergo detoxification from BUP/NLX for up to a 4-week period. Follow-up visits, scheduled at 1, 3, and 6 months after study completion, will evaluate the durability of treatment effects on drug use and psychosocial outcomes.

Entry into Treatment: Triage will be done by a staff member and will take about 30 minutes. It will cover basic inclusion and exclusion criteria, as well as a brief description of the study, to determine if the subject is interested in participating. Treatment alternatives as described below will also be offered to the prospective subject. If s/he is appropriate and agrees to participate, full screening will be completed. Screening will be done by a research assistant and a clinician and take about 3 hours. During this time informed consent will be obtained, an explanation of the study will be provided, and evaluation of inclusion and exclusion criteria will be done. Laboratory examination will include ECG and complete blood count, serum electrolytes, BUN/Creatinine, liver and thyroid function tests, PT, PTT, RPR, random glucose, urinalysis and urine toxicology. A psychiatric evaluation and physical exam will be performed by a study physician, which will take an additional hour. In addition, a SCID utilizing DSM-V criteria will be completed. Should a subject present already in withdrawal and need to be started on BUP/NLX before lab results return or SCID can be completed, the SCID sections that address eligibility will be completed, and the rest will be completed within a week. The subject will also be given an intake package of questionnaires to complete.

Buprenorphine: Buprenorphine is available alone or in combination tablet containing buprenorphine and naloxone in a ratio of 4:1 (Johnson et al., 2003). In prescription-opioid dependent patients who are treated with BUP/NLX, the most common daily doses are 12 and 16

mg/day. In this study, a combination tablet will be used, since it is less likely to be diverted than the buprenorphine only formulation. Consistent with the clinical guidelines, before BUP/NLX is administered, participants will be instructed not to use any prescription opioids for 24 hours and be prepared to stay in the clinic for at least 2 hours following the first dose of BUP/NLX. On the induction day, participants in the low dose group will start with 2/5 mg but may receive a maximum of 4/1 mg of BUP/NLX, and will be assessed by a physician in the clinic for up to 2 hours for signs and symptoms of opioid withdrawal. Participants in the high dose group will also start with a 2/5 mg but may receive additional doses of BUP/NLX on the induction day if initial BUP/NLX doses do not suppress opioid withdrawal adequately. Between days 2 and 5, the dose may be gradually increased to the target dose based on the response of the patient: (1) low dose subjects will be held as low as tolerated with a maximum of 8 mg and (2) high dose subjects will be increased to at least 16 mg. At the end of the trial, subjects will receive *up to* a four-week buprenorphine taper depending on individual needs. Buprenorphine/Naloxone is a Schedule III drug that, in community settings, is often prescribed for up to a one month's supply at a time. Patients are generally seen on a weekly or monthly basis like those treated with other psychiatric medications. Buprenorphine/Naloxone will be delivered by the research pharmacy on the day of the participant's weekly appointment, and will be returned to the research pharmacy should the subject fail to present for the appointment. Buprenorphine/Naloxone treatment is generally well tolerated. Its side effects, such as abdominal pain, constipation, nausea, vomiting, headache, sweating, sedation, and allergic reaction are similar to other opioids. Increases in liver enzymes and hepatitis are rarely reported. Participants will be educated to keep their medication in a safe place to prevent unintentional exposure to others, especially children.

Medical Management: Medical Management (MM) will be provided for all patients in the study. It is a behavioral intervention designed for patients with alcohol dependence (Pettinati et al. 2000), and similar therapies have been used in other drug abuse trials (Weiss et al. 2011). The objective of MM is to approximate a primary care environment for delivering care for substance dependent patients. In this study MM will be provided by a trained registered nurse and will consist of 12 sessions. The initial visit will be 40-60 minutes and the focus will be on discussing negative consequences of substance use, and educating the patient on medication regimen and compliance. Consecutive sessions will be 15-20 minutes and will be focused on relapse prevention, monitoring of compliance with the medication and psychoeducation. Common elements of the sessions will be identification of high-risk situations and warning signs of relapse. Patients will be encouraged to attend support groups in the community (e.g. Narcotics Anonymous). This intervention was chosen because MM's focus on medical issues is highly compatible with a pharmacologic intervention.

Medication Compliance: In addition to MM we employ a number of strategies to insure maximum compliance with the medication regimen. All medications will be dispensed in clearly labeled prescription vials. During the induction phase all medication will be handled by the nurses on the detox unit. After that all visits and medication dispensing will be done by out nurse ([name]). Before each visit each patient will receive a reminder phone call about his appointment and is also reminded to return the bottle with the study medication regardless of whether any medication is left over. At the beginning of each study visit the left over medication will be counted and the patient will be prompted to report any doubling of dose or missing days of study medication. The session will also provide an opportunity for subjects to review critical

issues and problem areas, the subjects' involvement in any ancillary treatments, and other clinically significant events. Other formal treatment concurrent with their study treatment (including self-help meetings) will be monitored and will be included as a covariate in the analysis.

Use of other drugs of abuse and program termination: At every clinic visit, the subjects will be asked to take a breathalyzer test as a measure of the blood alcohol levels. Subjects will be asked not to use alcohol throughout the study since alcohol may interact with BUP/NLX causing CNS toxicity and respiratory depression. If a breathalyzer reading is 0.04 or greater, the buprenorphine dose will be held until the breathalyzer reading falls below 0.04. If the breathalyzer levels do not fall below 0.04 until the dispensing hours end, subjects will not receive BUP/NLX for that day. If the reading is between 0.01 – 0.04, the subject will receive one-half of their BUP/NLX dose. If the level falls below 0.01 prior to close of dispensing that day, the subject can receive a full dose. If the breathalyzer reading is over the legal limit, 0.08 or more, the study physician will be notified. If the study physician determines that it is unsafe for the participant to leave the clinic, the participant may be taken to the Psychiatric Emergency Room for further evaluation and treatment.

During the final phase of the study, we estimate that approximately 20% of participants will opt for detoxification. In those cases, we will provide a detoxification or a two to four-week taper from buprenorphine depending on each individual's needs. Subjects will then be referred to appropriate outpatient substance abuse treatment (abstinence based). The rest of the subjects will likely request to continue on buprenorphine maintenance. We will refer those patients to the VA clinic.

At any point in the study, subjects will be withdrawn if they regularly miss medications (2 weeks in a row). Subjects may also be withdrawn from the program if urine toxicology screens show frequent use of benzodiazepines or barbiturates. Subjects withdrawn from the study will be offered detoxification from buprenorphine, possibly for naltrexone treatment or referral to methadone maintenance. Subjects will also be withdrawn from the study if the investigator has evidence that subjects' health or well-being may be threatened by continuation in the study. Should a pregnancy test become positive, the subject will be withdrawn from the study and referred to an appropriate treatment program.

Assessments: Trained research assistants and clinical staff will meet with the subject at various time-points to assess the subject on selected substance use and psychological functioning measures using structured interviews, self-report assessments, and to obtain urine samples for toxicology screens.

The following assessments will be completed at baseline:

1. Brief Pain Inventory-Short Form
2. Center for Epidemiologic Studies Depression (CES-D) scale
3. Clinical Opiate Withdrawal Scale
4. Columbia-Suicide Severity Rating Scale (C-SSRS)
5. Drug Use Inventory
6. Fagerstrom Tolerance questionnaire for determination of nicotine dependence
7. Medical and Psychiatric Evaluation (including laboratory blood work and EKG)
8. Post Traumatic Stress Disorder Checklist (PCL-C)

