 - Center for Epidemiologic Studies Depression (CES-D) scale: CES-D is a 20-item self-report measure of depressive symptoms. The range of scores is from 0 to 60, higher scores reflecting increased depressive symptoms. The CES-D does not heavily depend on pathological items compared with other scales such as Beck Depression Inventory and does not define clinical depression. The CES-D has been shown to be a reliable and valid scale, and it has been used in several epidemiological studies including cocaine users (Bobo et al., 1998; Orme et al., 1986; Weissman et al., 1977). This measure will be obtained at baseline and weekly thereafter.
 - Clinical Opiate Withdrawal Scale (COWS): Withdrawal signs and symptoms will be assessed using a 22-item withdrawal instrument that has been reliably used to assess opiate withdrawal. This scale rates the following items from 0 to 4: lacrimation, nasal congestion, yawning, sneezing, coughing, throat clearing, restlessness, nausea/vomiting, gooseflesh, sweating, stomach cramps, muscle cramps, and feeling hot/cold. This scale will be used on a weekly basis.
 - Columbia-Suicide Severity Rating Scale (C-SSRS): designed to assess suicidal ideation and suicidal intent.
 - Fagerstrom Nicotine Tolerance Questionnaire (FNTQ): This self-report measure assesses the degree of nicotine dependence and has been used widely in smoking studies (Fagerstrom, 1978). This instrument has demonstrated reliability and validity (Pomerleau et al., 1994; Tate and Schmitz, 1993).
 - Post Traumatic Stress Disorder Checklist (PCL-C): to measure PTSD symptoms. The PCL-C is a self-report scale that shares similar reliability with the CAPS. (Weathers et al. 1996)
 - Structured Clinical Interview for DSM-V (SCID) will be used to obtain DSM-V Opiate use dependence, and other Substance Use Disorder diagnoses. The number of dependence syndrome elements endorsed from the DSM-V criteria will assess severity of opiate and other substance use. This instrument will be administered at baseline or in as timely a manner as patient's condition warrants.
 - Time Line Followback: At intake and weekly thereafter, assessments will be made of opioid and other drug use.
 - Weekly cigarette smoking: At intake and weekly thereafter, self-reports will also be made on cigarette smoking.

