- C. SAFTEE: The SAFTEE is a technique for the systematic assessment of side effects in clinical trials. The SAFTEE will be reviewed by the study nurse and specific symptoms, as well as severity, will be recorded. The SAFTEE will be administered weekly.

Data Analysis Methods:

A. Sample Size and Power Analysis:

For this pilot study, we will recruit a total of 200 subjects, 100 subjects in each treatment arm. No previous studies have examined the influence of BUP/NLX dose on treatment outcomes in prescription-opioid dependent individuals. Our sample of 200 will require an effect size of .25 to detect differences between the two treatment groups for the number of opioid positive urines during the treatment period.

B. Statistical analysis:

The principal analyses will be done on the modified intention to treat sample, that is, subjects receiving at least one dose of BUP/NLX. First, we will determine the success of the randomization by comparing the two treatment groups on socio-demographic and baseline clinical characteristics using chi-square for categorical variables and ANOVA for continuous variables. Second, survival analysis will be used to determine differences between experimental groups in treatment retention. Third, random regression analyses (HLM), (Hedeker and Gibbons 1996) will be conducted to examine if the change in opioid use behavior over time varies as a function of the treatment factors.

Risks and Benefits:

Potential risks

1. Buprenorphine: Buprenorphine, formulated as a sublingual tablet, is available alone or in combination tablet containing buprenorphine and naloxone in a ratio of 4:1. The doses of buprenorphine/naloxone used here are within the recommended guidelines of the manufacturer (4-24 mg/day). In this study, combination tablet will be used, since it is less likely to be diverted than the buprenorphine alone formulation. Common side effects of buprenorphine/naloxone include abdominal pain, constipation, nausea, vomiting, headache sweating, sedation, and allergic reaction. Uncommon but more serious adverse effects of buprenorphine/naloxone include hepatic abnormalities, orthostatic hypotension and respiratory depression.
2. Buprenorphine/Naloxone detoxification: Detoxification from buprenorphine/naloxone can produce signs and symptoms of opiate withdrawal, including nasal congestion, abdominal symptoms, anxiety, myalgia, insomnia, sweating, and diarrhea.

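### The plan adjusts the analysis for concurrent treatment and self-help attendance, which is measured after open-label randomization and can bias the dose comparison

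*Combined protocol and SAP*

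**What the plan says.** Under Medication Compliance, the protocol commits without qualification: "Other formal treatment concurrent with their study treatment (including self-help meetings) will be monitored and will be included as a covariate in the analysis". The sentence before it places the data collection at study visits, which review "involvement in any ancillary treatments, and other clinically significant events". The covariate is therefore a post-randomization measurement. It can also change during the trial, because Medical Management says: "Patients will be encouraged to attend support groups in the community (e.g. Narcotics Anonymous".

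The Research Plan is explicit about blinding: "This will be a randomized, open-label clinical trial". It also contains one rule that differs by arm and affects time on study. It applies to a participant who is "randomized to the low dose group but is experiencing withdrawal symptoms that cannot be stabilized the participant will be discharged from the study".

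The Statistical analysis section lists the principal analyses. For retention, "survival analysis will be used to determine differences between experimental groups in treatment retention". For opioid use, random regression (HLM) is to "examine if the change in opioid use behavior over time varies as a function of the treatment factors". That section names no covariates, excludes none, and does not state that the dose comparison is unadjusted.

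**The concern.** Randomization balances what exists before assignment. Attendance during treatment comes later, and in an open-label trial it may respond to the dose or to knowing the dose. Conditioning on it then does two things. It blocks any part of the dose effect that runs through attendance. It also makes the arms non-comparable on unmeasured traits, such as severity or motivation, that drive both attendance and outcome. In either case the adjusted coefficient need not be the randomized comparison.

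Retention has a further problem. A cumulative count of meetings grows with time on study, so as a fixed covariate it is partly determined by the outcome.

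The plan names no outcome, model or coding for the covariate. Whether and how to adjust could therefore be settled after open-label data have been seen.

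**Working it through.** **The plan's own figure.** The only number in the analysis section is 200 participants (100 per arm) with an effect size of .25. Alpha, power and metric are not given. At two-sided .05 (assumed), power = Φ(d√(n/2) − 1.96). Read as d = .25: .25 × √50 = 1.77, power 42%. Read as f = .25 (d = .50): 3.54, power 94%. The detectable d at 80% power is (1.960 + .842) × √(2/100) = .396. The figure cannot be confirmed or refuted, and the point here does not depend on it.

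**Inputs.** From the documents: 100 per arm, open label, 12 weeks, a post-randomization covariate. Every association below is assumed, because the documents give none.

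**1. One total per person (for example, number of positive urines).** Let A be arm, U an unmeasured trait, M attendance and Y outcome, with unit variance within arm:

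- M = aA + pU + error
- Y = τA + mM + qU + error
- Total dose effect = τ + am
- Coefficient on A adjusted for M = τ − apq
- Bias = −a(m + pq)
- SE² ≈ [1 − (m + pq)²] × [2/100 + a²/198]

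Example with a = .8, p = q = .6, m = 0: bias = −.8 × .36 = −.288. SE = √(.8704 × .02323) = .142. The ratio is 2.03 and rejection is about 52%. Simulated rejection with no true total effect:

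| a | m | p = q | Bias (SD) | Rejection |
|---|---|---|---|---|
| 0 | 0 or .3 | various | 0 | 4.9% to 5.3% |
| .3 | 0 | .3 | −.027 | 5.5% |
| .3 | 0 | .6 | −.108 | 12.6% |
| .5 | 0 | .5 | −.125 | 13.7% |
| .8 | 0 | .6 | −.288 | 53.0% |
| .4 | .3 | 0 | −.120 | 14.7% |
| .2 | .3 | .4 | −.092 | 11.2% |
| .4 | .3 | .4 | −.184 | 30.2% |

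Rows with m = 0 show the shared-cause path alone. The row with p = q = 0 shows mediation alone. The last two rows combine them. In the scenarios that include m = .3, and in the a = .4, p = q = .4 case without it, the unadjusted test rejected 4.4% to 5.5%.

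With a true effect of −.40 SD, p = q = .6 and m = 0, a = +.8 gives −.40 − .288 = −.688 and a = −.8 gives −.40 + .288 = −.112. Simulated values were −.686 (power 99.6%) and −.111 (11.8%). With a true effect of .25 SD, m = .3 and p = q = .4, a = .4 gives .25 − .184 = .066 and a = −.4 gives .434.

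**2. Mixed model, group-by-time test.** Settings: 12 visits, random intercept SD 1, slope SD .1, residual SD 1, complete data. Entering M only as a person-level main effect changes nothing: in one dataset the arm-by-time coefficient was −.01055 with and without it. Adding M-by-time moved it to −.04117. Over three settings, (a, p = q) = (.3, .3), (.5, .5) and (.8, .6), type I error was 5.1%, 10.4% and 32.0% with M-by-time. With weekly attendance as a time-varying covariate it was 5.0%, 10.5% and 32.6%.

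**3. Retention, Cox model, total meetings as a fixed covariate.** Settings: exponential dropout, true hazard ratio 1, 50% to 80% retained at week 12, mean one meeting per week, coefficient of variation of the person's rate 1.

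- Equal attendance rates by arm: hazard ratio 1.00, error 4.9% to 5.8%.
- Rate ratio .5: hazard ratio .76, error 27.6%, 21.4% and 13.2% at 50%, 65% and 80% retained.
- Rate ratio 2: hazard ratio 1.32 to 1.35, error 29.0%, 23.2% and 13.8%.
- Meetings per week on study instead (50% and 65% retained): error 4.2% to 5.6%.

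**4. The documented route from arm to attendance.** If 10%, 20% or 30% of the low-dose arm were discharged at week 1, with equal weekly rates of .5 to 2 meetings, total attendance would shift by about .09, .18 and .26 to .28 SD. In case 1 with m = 0 and p = q between .3 and .6, a shift of .09 gives error of about 5% to 6%, and .28 gives about 5% to 12%.

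**The case against.** The strongest reply is that the commitment sits in a compliance paragraph and says only that the covariate enters the analysis. The section that defines the principal analyses names no covariate, so they may be meant as unadjusted. That reading is possible, but nothing in the plan states it, and the only sentence that addresses the matter points the other way. Two tenable readings are themselves a gap in pre-specification.

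Second, the plainest versions of the planned analyses may be unharmed. This largely stands. A person-level main effect leaves the group-by-time test alone. With outcome-dependent dropout at the strongest setting (500 runs), rejection was 4.0% with the covariate and 5.6% without. A log-rank test takes no covariate. The retention inflation needs a Cox model, a raw count and unequal attendance; it arises because the count grows with follow-up. The plan rules out none of these choices.

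Third, the largest figures come from a per-person total, which the plan uses only in its power statement, and from strong assumed associations. That is correct, and they should be read as the upper end of an illustration.

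Fourth, support-group encouragement is given to both arms, so the discharge rule is the only documented route from arm to attendance, and its effect alone is small. For retention, that discharge is also part of the outcome itself. Both points stand. The open-label design still leaves other routes possible.

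Finally, the plan calls this a pilot study. That lowers the stakes but does not make the adjusted estimate the randomized comparison.

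**Conclusion.** The concern holds: the plan commits to adjusting for a variable measured after open-label randomization and does not keep that adjustment out of the primary dose comparison. This can bias the comparison; it need not. Bias requires that arm affects attendance and that attendance either affects the outcome, shares causes with it, or, for a cumulative count in the retention model, is partly determined by it. Sign and size cannot be obtained from the documents. Under the assumed ranges, error at a nominal 5% runs from essentially 5% to about 52% for a per-person total, 5% to about 33% for the mixed model with attendance-by-time or weekly attendance, and 13% to 29% for a Cox model on total meetings with a two-fold difference in rates. It stays near 5% when attendance does not depend on arm, and under the harmless codings described above. The potential distortion is large relative to the cost of preventing it, so this should be fixed.

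**What to change.** Replace the covariate sentence under Medication Compliance, and add to Statistical analysis, a statement such as:

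> *The primary comparisons of retention and opioid use are not adjusted for concurrent treatment or self-help attendance, which is reported by arm.*

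If an adjusted analysis is wanted, label it sensitivity or exploratory and fix its outcome, model and coding in advance. For retention, do not enter a raw cumulative count as a fixed covariate.

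Any covariate in the primary models should be measured before randomization. Baseline opioid use is already available: "Time Line Followback: At intake and weekly thereafter, assessments will be made of opioid and other drug use". Its gain in precision depends on a correlation the documents do not give, so including it is optional.

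The cost is wording in two sections. No new data are needed and the sample size does not change.
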